### **Pediatric Asthma Symptom Questionnaire (PASQ)**

The PASQ is a questionnaire developed by the sponsor to monitor asthma control in preschool children in clinical trial settings. The advantage of the PASQ is the much shorter recall period for various items to fit the schedule of clinical trials and improvement in ability to recall as compared to existing instruments. The questionnaire consists of 6 questions related to asthma control.

The questionnaire will be completed only for the subset of patients with ongoing asthma. It is to be completed by the child's parent or caregiver who fluently speaks a language in which the questionnaire is presented, at time points according to [Appendix 3](#). It is recommended that the same person complete the questionnaire on behalf of the patient throughout the study. Questions 4, 5, and 6 will only be answered if the answer to Question 3 is > 0 days. Higher score indicates worse condition (asthma severity).

The following algorithm will be implemented to calculate PASQ score.

- Questions 1 & 2 should still be calculated and summarized separately.
- For questions 3 to 6 (ranged from 0 to 4), total score, which can be termed as PASQ score. will be calculated.
  - If answer to question 3 is 0, then the total score is 0, regardless of answers to questions 4-6;
  - If answer to question 3 is non-zero and answers to questions 4 to 6 are all 0, then the total score will be equal to the score for question 3;
  - If answer to question 3 is non-zero and answers to questions 4 to 6 are also non-zero values, then the total score is calculated by adding the scores for questions 4 to 6; Also ignore the score in question 3.

Handling missing items from PASQ:

If answer to question 3 is missing and answers to questions 4-6 are non-missing, then the total score is calculated by adding the scores for questions 4 to 6; if one item from questions 4 to 6 is missing, set the score of the missing item as the average of the other two non-missing items from questions 4-6 and calculate total score. If two or more items from questions 4-6 are missing, then set the total score as missing.

If answer to question 3 is non-missing and non-zero, and if one item from questions 4-6 is missing, set the score for the missing item as the average of the other two non-missing items from questions 4-6 and calculate total score. If two or more items from questions 4-6 are missing, then set the total score as missing.

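### The PASQ scoring rule breaks the SAP's own direction statement on either reading: it leaves 60 of 125 item patterns unscored with one reversal, or scores every complete pattern with 31 reversals in 496

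*SAP*

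**What the plan says.** SAP Section 4.4.3 sets out how the PASQ is scored. The direction is stated as "Higher score indicates worse condition (asthma severity". The item range and the name of the total come from "For questions 3 to 6 (ranged from 0 to 4), total score, which can be termed as PASQ score". A skip rule applies: "Questions 4, 5, and 6 will only be answered if the answer to Question 3 is > 0 days".

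Three bullets define the total:

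- **First.** "If answer to question 3 is 0, then the total score is 0, regardless of answers to questions 4-6".
- **Second.** With Q3 non-zero, if "answers to questions 4 to 6 are all 0, then the total score will be equal to the score for question 3".
- **Third.** With Q3 non-zero, if "answers to questions 4 to 6 are also non-zero values, then the total score is calculated by adding the scores for questions 4 to 6". The bullet closes with "Also ignore the score in question 3".

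Two further paragraphs deal with unanswered items. If Q3 is missing and Q4-Q6 are answered, the total is their sum. If one of Q4-Q6 is missing, it takes the average of the other two.

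No other place gives a scoring rule. Protocol Section 6.2.2.18 says only that there are six questions on asthma control and that the instrument is in the investigator site binder. SAP Appendix 2 says the total uses questions 3 to 6 and is analysed by ANCOVA after the MI-WOCF imputation.

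**The concern.** A severity score should cover every set of answers the form can produce, and it should not go down when one answer gets worse and none gets better. The three bullets do not clearly meet the first condition and do not meet the second.

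The second bullet takes the score from Q3 and the third discards Q3, so the total can drop at the point where Q4-Q6 leave zero. Answers to Q4-Q6 that mix zeros and non-zeros fit the third bullet only if its condition is read as any item rather than every item.

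The SAP lists change from baseline to week 16 in PASQ as an endpoint. A child whose answers worsen could record a negative change, which counts as improvement. Two programmers following the same text could also give the same child different scores.

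**Working it through.** The documents give no figure for PASQ scoring, so there is none to reproduce. The check is an enumeration.

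**Inputs.** From SAP Section 4.4.3: items Q3 to Q6 range from 0 to 4, taken here as five integer levels each; the skip rule; the three bullets. Patterns are written (Q3,Q4,Q5,Q6).

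**Patterns the form can produce.** Q3 = 0 gives one pattern. Q3 = 1 to 4 gives 4 × 5³ = 4 × 125 = 500. The total is 501.

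**Reading A: the third bullet needs Q4, Q5 and Q6 all non-zero.**

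- For each non-zero Q3, one pattern is all zero and 4³ = 64 are all non-zero. The rest, 125 − 1 − 64 = 60, match no bullet (60/125 = 48.0%).
- Over the four non-zero values of Q3, 4 × 60 = 240 patterns are unscored, or 240/501 = 47.9% of those the form can produce. The other 261 are scored.
- The smallest sum the third bullet can give is 1 + 1 + 1 = 3. It falls below a second-bullet score only when that score is 4. Comparing every pair of scored patterns in which one is at least as high on all items and higher on at least one, exactly one reversal appears: (4,0,0,0) = 4 against (4,1,1,1) = 3.

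**Reading B: the third bullet needs at least one of Q4-Q6 non-zero.**

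- All 501 complete patterns are scored.
- There are 4 × 124 = 496 combinations with Q3 above 0 and at least one of Q4-Q6 non-zero. Each is compared with the same Q3 and Q4-Q6 all 0, which scores Q3.
- Q4-Q6 sums of 1, 2 and 3 arise in 3, 6 and 10 ways.

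| Q3 | Q4-Q6 sums below Q3 | Combinations |
|---|---|---|
| 1 | none | 0 |
| 2 | 1 | 3 |
| 3 | 1, 2 | 3 + 6 = 9 |
| 4 | 1, 2, 3 | 3 + 6 + 10 = 19 |
| Total | | 31 of 496 (6.3%) |

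- The largest drop is 3 points: (4,0,0,0) = 4 against (4,1,0,0) = 1. If Q3 may also rise between the two patterns, the number of reversed pairs is 46.

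**Missing Q3.** With Q3 missing and Q4-Q6 all 0, the sum rule gives 0. With the same answers and an observed non-zero Q3, the second bullet gives 1 to 4. Under the skip rule, answered Q4-Q6 imply that Q3 was above 0, so 0 is lower than any score the child could have had.

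**Candidate replacement.** Total = 0 if Q3 = 0, otherwise max(Q3, Q4+Q5+Q6). Over the 501 patterns it leaves none unscored and gives no reversals. With Q4-Q6 all 0 it returns Q3, as now. With all three non-zero the sum is at least 3, so it differs from the present value only when Q3 = 4 and the sum is 3. That is (4,1,1,1), which moves from 3 to 4.

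**The case against.** The strongest reply is that the third bullet is simply the complement of the second: if the items are not all zero, add them. The missing-Q3 paragraph supports this, because it sums Q4-Q6 without asking that each be non-zero. On that reading nothing is unscored. This stands as a fair reading, so the gap should be called a consequence of the literal text and not a settled fact. It does not rescue the rule, because it is the reading with 31 reversals instead of one.

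A reader might combine the two large counts and infer that nearly half the patterns are unscored and that dozens of reversals occur as well. The documents do not support that, because the counts belong to alternative readings.

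A reader might also infer that close to half of the children with asthma would go unscored. That does not follow either. Each pattern is counted once, while real answers are probably correlated, and no response frequencies are given.

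Finally, the wording of Q3 to Q6 is not in the documents. Whether (4,1,1,1) is clinically worse than (4,0,0,0), or how often either occurs, cannot be judged here. What is shown is a formal conflict with the SAP's statement of direction.

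**Conclusion.** The scoring rule is wrong as written, because neither reading satisfies the stated direction. Read literally, it leaves 60 of 125 Q4-Q6 patterns without a score for each non-zero Q3 and has one reversal of 1 point. Read loosely, it scores every complete pattern but has 31 reversals in 496, of up to 3 points.

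This rests on two assumptions: integer levels 0 to 4 on each item, and a higher answer on each item being worse, as the direction statement implies. The share of children affected is unknown.

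The consequence is small. Section 4.4.3 lists PASQ change as exploratory, and only children with ongoing asthma complete the form. It is absent from the hierarchy in SAP Section 5.6.3, and Appendix 2 plans no sensitivity or subgroup analysis of it. It would be a mistake to infer doubt about any primary, key secondary or hierarchy-controlled result. The point is worth correcting, but it is minor.

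**What to change.** Before database lock, replace the three bullets in SAP Section 4.4.3 with one rule that covers every complete pattern and never falls as items worsen. One option is: *PASQ total = 0 if Q3 = 0; if Q3 > 0, the larger of Q3 and Q4+Q5+Q6.* The plain sum Q3+Q4+Q5+Q6 also has no gaps or reversals, but it changes many more of the currently defined values. Confirm the choice against the sponsor's scoring instructions for the instrument, which are not in the documents.

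Align the missing-Q3 paragraph at the same time. Under the max rule, a Q4-Q6 sum of 4 or more fixes the total whatever Q3 was, since Q3 cannot exceed 4. A smaller sum does not, so the SAP should say how those cases are handled, including Q4-Q6 all 0, which now scores 0.

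The cost is a short SAP edit and a programming change. The downsides are that it alters the sponsor's own scoring rule and that the max rule does not register low Q4-Q6 scores when Q3 is high: (4,0,0,0), (4,1,1,1) and (4,2,1,1) all score 4.

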### **Caregiver-Reported Nasal Symptom Questionnaire (CNSQ):**

The CNSQ will be used to assess the effect of study drug on symptoms of allergic rhinitis. The summed score will include the following 4 symptoms: runny nose, nasal congestion, nasal itching, and sneezing, each rated on a 0 to 3 scale of severity. The questionnaire will be completed only for the subset of patients with a medical history of allergic rhinitis. It is to be completed by the child's parent or caregiver who fluently speaks a language in which the questionnaire is presented (based on availability of translations in participating countries). Total score is the sum of all symptom scores. If there is one symptom score missing, the total score is set to missing. The minimum and maximum possible values of the total CNSQ score are 0 and 12. Higher score indicates worse condition.

Caregivers will be instructed on using the e-diary to record the CNSQ during the screening period (for the 14 days before baseline/day 1) and for the 7 days preceding visits for weeks 4, 16, and 28 as described in [Appendix 3](#).

The baseline CNSQ score is defined as the average of the CNSQ scores reported continuously for 7 days right before the baseline visit (i.e. study day -7 to day -1). The weekly average CNSQ score (post-baseline) will be calculated as the average of the available reported daily CNSQ score within 7 days prior to the visit. For example, if there are 3 scores available in a week, the average = (score1 + score2 + score3)/3.

## **4.5. Safety Variables**

### **4.5.1. Adverse Events and Serious Adverse Events Variables**

Adverse events and serious adverse events (SAE) will be collected starting from the time of informed consent signature and at each visit until the end of the study. All adverse events are to be coded to a "Preferred Term (PT)", "High Level Term (HLT)" and associated primary "System Organ Class (SOC)" according to the Medical Dictionary for Regulatory Activities (MedDRA).

The criteria for determining whether an abnormal laboratory, vital sign or ECG finding should be reported as an AE are as follows:

- Test result is associated with accompanying symptoms, and/or
- Test result requires additional diagnostic testing or medical/surgical intervention, and/or
- Test result leads to a change in dosing (outside of protocol-stipulated dose adjustments) or discontinuation from the study, significant additional concomitant drug treatment, or other therapy

The pre-treatment period is defined as the period from the patient providing informed consent up to the first dose of study drug. The treatment and follow-up period is defined as the period from the administration of first study dose to the EOS visit.

Pre-treatment AEs and treatment emergent AEs (TEAEs) are defined as follows:

- Pre-treatment AEs are AEs that developed or worsened in severity during the pre-treatment period.

- Treatment-emergent AEs (TEAEs) are AEs that developed or worsened in severity compared to the baseline during the treatment and follow-up period. As only worsening pre-existing AEs and new AEs reported during the treatment and follow-up period will be collected in the study, all AEs collected during the treatment and follow-up period are considered TEAEs.
- TEAEs during the 16 week treatment period are AEs with onset after the first dose up to the week 16 visit date (study day 113 if the week 16 visit date is missing) or early termination visit, whichever is earlier. TEAEs that have an onset during the 16 week treatment period and continued afterwards into the follow-up period will be counted only once as TEAEs during the 16 week treatment period.
- TEAEs during the follow-up period are AEs with onset after the week 16 visit date up to the end of the study.

**AEs of Special Interest (AESI):**

The following AESIs will be analyzed:

- Anaphylactic reactions
- Systemic hypersensitivity reactions
- Helminthic infections
- Any severe type of conjunctivitis or blepharitis
- Keratitis
- Clinically symptomatic eosinophilia (or eosinophilia associated with clinical symptoms)

**Other AEs:**

Skin Infections (with adjudication by clinical), Herpes Infections and Injection Site Reactions will be analyzed.

Additionally other AEs such as Narrow and Broad Conjunctivitis CMQ will be analyzed.

- **Narrow conjunctivitis** CMQ is defined as the following PT terms
  - Conjunctivitis
  - Conjunctivitis allergic
  - Conjunctivitis bacterial
  - Conjunctivitis viral
  - Atopic Keratoconjunctivitis
- **Broad conjunctivitis** CMQ is defined as the following PT terms
  - Conjunctivitis
  - Conjunctivitis allergic
  - Conjunctivitis bacterial
  - Conjunctivitis viral

- Atopic Keratoconjunctivitis
- Blepharitis
- Dry eye
- Eye irritation
- Eye pruritus
- Lacrimation increased
- Eye discharge
- Foreign body sensation in eyes
- Photophobia
- Ocular hyperaemia
- Conjunctival hyperaemia
- Xerophthalmia

Note that, [Appendix 4](#) provides a list of AESIs search criteria.

#### 4.5.2. Laboratory Safety Variables

Hematology, and chemistry samples will be analyzed by a central laboratory.

Samples for laboratory testing will be collected according to visit schedule ([Appendix 3](#)). Tests will include

##### Serum Chemistry

Sodium	Total protein, serum	Total bilirubin 
Potassium	Creatinine	Total cholesterol 
Chloride	Blood urea nitrogen (BUN)	Triglycerides
Carbon dioxide	AST	Uric acid
Calcium	ALT	CPK 
Glucose	Alkaline phosphatase	
Albumin	Lactate dehydrogenase (LDH)	

1 Direct and indirect bilirubin will be measured when the total bilirubin is above the ULN

2 Low-density lipoprotein and high-density lipoprotein

3 CPK isoenzymes will be measured when CPK >5× the ULN

### **Hematology**

Hemoglobin	Differential:
Hematocrit	Neutrophils
Red blood cells (RBCs)	Lymphocytes
White blood cells (WBCs)	Monocytes
Red cell indices	Basophils
Platelet count	Eosinophils

### **Other Laboratory Tests**

The following tests will be performed at screening: HIV, HBsAg, HBsAb, HBcAb, hepatitis C antibody, tuberculosis (will be performed on a country-by-country basis according to local guidelines if required by regulatory authorities or ethics boards). Serum samples for vaccination response will be collected at time points as described in [Appendix 3](#).

#### **4.5.3. Vital Sign Variables**

The following vital signs parameters will be collected:

- Respiratory rate (bpm)
- Heart rate (beats/min)
- Sitting systolic and diastolic blood pressures (mmHg)
- Body temperature (°C)

Patients will be monitored at the study site at certain dosing visits for a minimum of 2 hours after study drug administration. Vital signs (systolic and diastolic blood pressure, heart rate, respiration, and temperature) will be performed at 30 minutes ( $\pm 10$  minutes) and 2 hours ( $\pm 15$  minutes) post-injection. See [Appendix 3](#) for assessment time points.

#### **4.5.4. Body Weight and Height**

Body weight and height will be measured at time points according to [Appendix 3](#).

#### **4.5.5. Physical Examination Variables**

The physical examination variable values are dichotomized to normal and abnormal. A thorough and complete physical examination will be performed at time points according to the schedule described in [Appendix 3](#).

#### **4.5.6. 12-Lead Electrocardiography (ECG) Variables**

Standard 12-Lead ECG parameters include: Ventricular HR, PR interval, QRS interval, corrected QT interval (QTc Fridericia [QTcF] =  $QT/[RR^{0.33}]$ ) ECG status: normal, abnormal not clinically significant or abnormal clinically significant. See [Appendix 3](#) for assessment time points.

#### 4.6. Pharmacokinetic (PK) Variables

Serum samples for measuring functional dupilumab concentrations will be collected at time points according to [Appendix 3](#). PK parameters may include, but are not limited to  $C_{trough}$  and  $C_{trough,SS}$ .

#### 4.7. Immunogenicity Variables

The immunogenicity variables are ADA status, titer, NAb status and time-point/visit. Serum samples for anti-dupilumab antibody testing will be collected at time points according to the visit schedule described in [Appendix 3](#). Samples positive in the ADA assay will be analyzed for the presence of neutralizing antibody in the NAb assay.

- ADA Negative, defined as ADA negative response in the dupilumab ADA assay at all timepoints, regardless of any missing samples.
- Pre-existing immunoreactivity, defined as either an ADA positive response in the dupilumab ADA assay at baseline with all post first dose ADA results negative, OR a positive response at baseline with all post first dose ADA responses less than 4-fold of baseline titer levels.
- Treatment-emergent response, defined as an ADA positive response in the dupilumab ADA assay post first dose when baseline results are negative or missing. The treatment-emergent responses may be further characterized as Persistent, Indeterminate or Transient.
- Persistent Response – Treatment-emergent ADA positive response with two or more consecutive ADA positive sampling time points, separated by at least 12-week period (based on nominal sampling time), with no ADA negative samples in between, regardless of any missing samples.
- Indeterminate Response – Treatment-emergent ADA positive response with only the last collected sample positive in the ADA assay, regardless of any missing samples.
- Transient Response – Treatment-emergent ADA positive response that is not considered persistent or indeterminate, regardless of any missing samples.
- Treatment-boosted response, defined as a positive response in the dupilumab ADA assay post first dose that is greater than or equal to 4-fold over baseline titer levels, when baseline results are positive.

Maximum Titer categories (Maximum titer values) are provided below.

Low (titer <1,000)

Moderate (1,000 ≤ titer ≤ 10,000)

High (titer >10,000)

#### **4.8. Biomarkers Variables**

Biomarkers to be analyzed in this study are:

- TARC
- Total serum IgE
- Immunoglobulin profiling
- Antigen-specific IgE
- Lactate dehydrogenase (LDH) [which will be measured as part of the blood chemistry]

Serum samples for measurements of biomarkers to study the PD activity of dupilumab in pediatric AD patients will be collected at time points according to [Appendix 3](#).

### **5. STATISTICAL METHODS**

For continuous variables, descriptive statistics will include the following: the number of patients reflected in the calculation (n), mean, median, standard deviation, first quartile (Q1), third quartile (Q3), minimum, and maximum.

For categorical or ordinal data, frequencies and percentages will be displayed for each category.

All data will be summarized by 2 treatment groups (i.e., dupilumab 200/300 mg Q4W and placebo).

#### **5.1. Demographics and Baseline Characteristics**

Demographics and baseline characteristics will be summarized by treatment group for the FAS.

#### **5.2. Medical and AD History**

Medical history will be summarized by primary SOC and PT for each treatment group. The table will be sorted by decreasing frequency of SOC, followed by PT, based on the overall incidence across treatment groups. Medical history will be listed, sorted by treatment groups.

Information on conditions related to AD will be summarized and includes diagnosis of AD and AD treatment history, asthma, allergic conjunctivitis, allergic rhinitis, chronic rhinosinusitis, nasal polyps, eosinophilic esophagitis, food allergy hives and other allergies due to medications, animals, plants, mold, dust mites, etc..

All analyses will be based on the SAF population.

#### **5.3. Prior/Concomitant Medications/Procedures**

The number and proportion of patients taking prior/concomitant medications, prohibited medications and rescue medications will be summarized, sorted by decreasing frequency of ATC Level 2 and ATC level 4, based on the overall incidence for the combined dupilumab treatment group. Patients will be counted only once for each medication class (ATC level 2 and 4) linked to the medication.

The number and proportion of patients taking prior/concomitant procedures, prohibited procedures and rescue procedures will be summarized, sorted by decreasing frequency of SOC and PT based on the overall incidence for the dupilumab treatment group. Patients will be counted only once for each SOC and PT linked to the procedure.

The number and proportion of patients taking adjudicated rescue treatment (concomitant topical treatments (medium to high potency TCS/TCI), systemic immunosuppressants) and/or other treatments (emollients/ antihistamines) will also be summarized separately.

The compliance with protocol requirements for application of moisturizers (emollients) used from 7 days before the baseline visit to end of study, which is defined as the (number of days moisturizers used during the period) / (number of days within the period) x 100%, will be summarized by treatment group

In addition, the summary of prior/concomitant medications/procedures may be provided for subjects who were impacted by the COVID-19 pandemic and not impacted by COVID-19 pandemic in each study period. The summary will be performed for pre-, during, and post-COVID-19 periods for subjects impacted by COVID-19, if deemed appropriate. The COVID-19 periods are consisting of 'Pre COVID-19 period', 'Post COVID-19 period' and 'During COVID-19 period' using start date and end date of being affected by COVID-19 for each patient who are affected by COVID-19.

Kaplan Meier curves for time to first rescue use will be generated.

#### **5.4. Subject Disposition**

The following summaries will be provided for each treatment group and study total (unless otherwise specified):

- The total number of screened patients who signed ICF, along with reasons for screen failure (for study total only)
- The total number of randomized patients (patients who received a randomization number)
- The total number of patients in each analysis set
- The total number of patients who completed the study and discontinued the study with the reason of discontinuation (including COVID-19 related reasons)
- The total number of patients who completed the study treatment and discontinued the study treatment with the reason of discontinuation (including COVID-19 related reasons)
- The total number of patients who continued on to the pediatric open label extension study
- The total number of patients who entered into the follow-up period and their study completion status, with reason of discontinuation (including COVID-19 related reasons), if applicable

